4.3. Preclinical Information for CTP-543

[REDACTED] The CTP-543 Investigator's Brochure should be consulted for more detailed technical information, current discussion of nonclinical evaluations, and relevant information regarding the known safety profile of CTP-543 to date, and potential safety concerns based on known effects of ruxolitinib.

4.4. Clinical Information

4.4.1. Clinical Studies of CTP-543

To date, 3 clinical studies have evaluated CTP-543.

Two clinical studies with CTP-543 in healthy volunteers have been completed. Study CP543.1001 was a pharmacokinetic/pharmacodynamic study consisting of a first-in-human single ascending dose study and a sequential multiple ascending dose study. The objective of the study was to assess safety, tolerability, pharmacokinetics, and pharmacodynamics of CTP-543 in healthy volunteers. A total of 82 subjects were planned for the study; 32 subjects in 4 cohorts randomized at a ratio of 3:1 CTP-543 to placebo for the single ascending dose part (Part A), and thereafter, 50 subjects in 5 cohorts randomized at a ratio of 4:1 CTP-543 to placebo for the multiple ascending dose part (Part B). The doses studied in the single ascending dose study were 8 mg, 16 mg, 32 mg, and 48 mg. The doses studied in the multiple ascending dose study were 8 mg once daily, 8 mg twice daily, 24 mg once daily, 32 mg once daily, and 16 mg twice daily, dosed for 7 consecutive days.

[figure not shown]
The second clinical study CP543.1002, also performed in healthy volunteers was a single dose cross-over study to assess safety and tolerability and to compare the metabolite and pharmacokinetic profiles of CTP-543 versus ruxolitinib. A total of 12 subjects were enrolled in the study; 2 groups of 6 subjects each were dosed with either 15 mg of ruxolitinib (1 x 15 mg tablet) or 16 mg of CTP-543 (2 x 8 mg tablets) in period 1 who then crossed over to the alternate treatment for period 2.

A Phase 2 study CP543.2001, A Double-Blind, Randomized, Placebo Controlled Study to Evaluate the Safety and Efficacy of CTP-543 in Adult Patients with Moderate to Severe Alopecia Areata, is ongoing.

CP543.2001 is a double-blind, randomized, placebo-controlled trial of approximately 125 adults with moderate-to-severe alopecia areata. Patients were sequentially randomized to receive one of three doses of CTP-543 (4, 8, 12 mg twice daily) or placebo for 24 weeks.

[figure not shown]
Interim top line analysis for the 4 and 8 mg cohorts showed that the primary efficacy endpoint in the 8 mg twice-daily cohort was met with 47% of patients achieving a $\geq 50\%$ reduction in their overall SALT score from baseline compared to placebo ($p<0.001$) (Figure 2).

Figure 2: Primary Analysis: Responders at Week 24

For the 4 mg cohort, 21% of patients achieved a $\geq 50\%$ reduction in their overall SALT score from baseline, however these differences were not significantly different from placebo. In the primary analysis, the response observed in the 8 mg twice-daily dose was significantly different than the 4 mg twice daily dose ($p < 0.05$) (Figure 3). The average baseline SALT score across all patients enrolled in the trial was approximately 88.

Figure 3: Primary Analysis: Responders by Visit

CTP-543 was generally well tolerated and there have been no serious adverse events reported. The most common adverse events reported across treatment groups (4 mg, 8 mg, and placebo)

were headache, upper respiratory tract infection, cough, acne and nausea. For the upper respiratory tract infections, there was a higher incidence in the placebo group. In terms of hematologic changes, there were only 3 incidents of Grade 3 or 4 changes and these 3 cases were distributed equally across the dose groups including placebo.

The 12 mg dosing cohort is currently ongoing.

5. ETHICS

The procedures set out in this study protocol, pertaining to the conduct, evaluation and documentation of this study, are designed to ensure that the Sponsor and the Investigator abide by Good Clinical Practice (GCP), including but not limited to Title 21 Code of Federal Regulations (CFR) Parts 50, 56, and 312, and the International Conference on Harmonisation (ICH) guidelines and directives. Compliance with these regulations also constitutes compliance with the ethical principles described in the current revision of the Declaration of Helsinki and applicable local regulatory requirements and law.

The Investigator is responsible for protecting the rights, safety, and welfare of patients under his/her care, and for the control of the medications under investigation. All ethical, regulatory, and legal requirements must be met before the first patient is enrolled in the study.

5.1. Institutional Review Board (IRB)

The Institutional Review Board (IRB) will meet all FDA requirements governing IRBs according to CFR, Title 21, Part 56. The Investigator (or designee) must submit this study protocol and any amendments, the Sponsor's approved informed consent form(s) (ICF), patient information sheets, patient recruitment materials, and other appropriate documents to the IRB for review and approval. Following review of the submitted materials a copy of the written and dated approval/favorable opinion will be forwarded to the Sponsor (or designee).

Any advertisements used to recruit patients for the study will be reviewed by the Sponsor and the IRB prior to use.

5.2. Written Informed Consent

Prior to performing any study-related activities under this protocol, including screening tests and assessments, written informed consent with the approved ICF must be obtained from the patient.

The ICF, as specified by the clinical site's IRB, must follow the Protection of Human Subjects regulations listed in the Code of Federal Regulations, Title 21, Part 50. The background of the proposed study, the procedures, the benefits and risks of the study, and that study participation is voluntary must be explained to the patient. The patient must be given sufficient time to consider whether to participate in the study.

A copy of the ICF, signed and dated by the patient, must be given to the patient. Confirmation of a patient's informed consent must also be documented in the patient's source documentation prior to any testing under this protocol, including screening tests and assessments. The original signed consent form will be retained with the study records.

All ICFs used in this study must be approved by the appropriate IRB and by the Sponsor. The ICF must not be altered without the prior agreement of the relevant IRB and the Sponsor.

6. STUDY OBJECTIVES

The overall objective of the study is to compare the efficacy and tolerability of a 16 mg total daily dose of CTP-543 utilizing two different dosing regimens in adult patients with chronic, moderate to severe alopecia areata.

[figure not shown]
The secondary/exploratory objectives of the study will be to assess the patient reported outcomes of hair coverage and hair coverage quality.

6.3 Study Design

This is a randomized, parallel group multicenter study to evaluate the efficacy and tolerability of two dosing regimens of CTP-543 (8 mg BID vs 16 mg QD), in adult patients with chronic, moderate to severe alopecia areata. Patients will be between 18 and 65 years of age and experiencing an episode of alopecia areata lasting at least 6 months and not exceeding 10 years, with at least 50% hair loss as measured by the SALT at Screening and Baseline, and are not concurrently being treated for alopecia areata with other treatments that might affect hair regrowth or immune response. Up to approximately 75% of alopecia areata patients with alopecia totalis or universalis, and no more than 10% with only alopecia ophiasis will be enrolled.

Patients may be screened up to 28-days prior to initiation of study drug. The Treatment Period is a 24-week dosing period where patients will be randomized to receive either CTP-543 8 mg BID, or CTP-543 16 mg QD and will be analyzed for the primary endpoints of the study. To minimize bias in the evaluation of study endpoints, patients, investigators, and site personnel will be unaware of the active drug dosing regimen by administering one 16 mg tablet and one placebo tablet 12 hours apart from each other for the 16 mg QD study group.

Figure 4: Study Design

Patients will provide informed consent prior to completing any screening procedures.

Patients will take the first dose of study drug in the clinic on Day 1. Patients will be instructed to take study drug every 12 hours. Patients should dose study drug in the clinic on all Study Visit Days after clinical laboratory blood draws are completed.

Patient safety will be monitored throughout the trial. The subject will be tested to ensure they do not have the Hepatitis B or C virus, thyroid function abnormalities or latent or active Tuberculosis, during the screening period. During the first 8 weeks of the Treatment Period, hematology and serum chemistry will be conducted every 2 weeks, followed by an assessment every 4 weeks thereafter through completion of the study at 24 weeks. Lipid levels will be assessed every 12 weeks throughout the Treatment Period. Significant cytopenias or other hematologic abnormalities will be managed by severity through dose interruption, or discontinuation, and signs and symptoms of infection will be closely monitored and treated promptly. Patients who experience intolerable symptoms during treatment may discontinue the study at the discretion of the Investigator. Patients may withdraw consent at any time.

The Treatment Period will last 24 weeks to assess BID and QD doses, in parallel. Assessment of treatment response with SALT for efficacy will occur at 4, 8, 12, 16, 20 and 24 weeks.

Upon completion of the 24-week Treatment Period patients will be eligible to either complete treatment and exit the study following the safety follow-up visit, or roll-over into a long-term open-label extension study.

Approximately 60 patients are planned to be enrolled in the study; approximately 30 patients per treatment arm.

6.4 Method of Treatment Assignment

Patients meeting screening criteria will continue to the Day 1 Randomization Visit for review of eligibility and baseline assessments, including SALT assessment, physical examination, clinical laboratory assessments, vital signs, and electrocardiogram. Patients meeting all eligibility criteria will be randomized to 1 of 2 CTP-543 treatment arms (8 mg BID or 16 mg QD).

Randomization will also be stratified by classification of alopecia areata subtype into one of the following three categories: 1) alopecia areata, 2) alopecia totalis or alopecia universalis, or 3) alopecia ophiasis.

7. SELECTION AND WITHDRAWAL OF PATIENTS

Patients eligible for enrollment in the study must meet all of the following inclusion criteria and none of the exclusion criteria.

7.1. Patient Inclusion Criteria

1. Written informed consent, and authorization for release and use of protected health information.
2. Between 18 and 65 years of age, inclusive, at the time of informed consent.
3. Definitive diagnosis of alopecia areata. Totalis or universalis and ophiasis subtypes must have a current episode lasting at least 6 months and not exceeding 10 years at the time of Screening. Total disease duration greater than 10 years is permitted.
4. At least 50% scalp hair loss, as defined by a SALT score ≥ 50 , at Screening and Baseline.
5. If of reproductive age, willing and able to use a medically highly effective form of birth control during the study and for 30 days following last dose of study medication.
Examples of medically highly effective forms of birth control are:
 - a. Surgical sterility (via vasectomy, hysterectomy or bilateral ligation) or post-menopausal females
 - b. Sexual partner is sterile, or of the same sex
 - c. Implants of levonorgestrel in females
 - d. Oral contraceptive (combined or progesterone only) in females
 - e. Double-barrier method (any combination of physical and chemical methods)
 - f. Intrauterine device in females or other method with published data showing that the lowest expected failure rate is less than 1% per year (not all intrauterine devices meet this criterion).
6. Willing to comply with the study visits and requirements of the study protocol.

7.2. Patient Exclusion Criteria

1. History or presence of hair transplants.
2. Treatment with other medications within 1 month of Screening or during the study that may affect hair regrowth or immunosuppression, such as: corticosteroids administered orally, by injection, or applied to areas of skin affected by alopecia; topical application of anthralin, squaric acid, diphenylcyclopropenone, or minoxidil.
3. Treatment with systemic immunosuppressive medications including but not limited to methotrexate, cyclosporine, and azathioprine; chloroquine derivatives; JAK inhibitors within 3 months of Screening (ruxolitinib, tofacitinib, etc), etanercept; or biologics (adalimumab, atlizumab, canakinumab, certolizumab, fontolizumab, golimumab, infliximab, mepolizumab, rituximab, secukinumab, tocilizumab, ustekinumab) within 6 months of Screening.
4. Active scalp inflammation, psoriasis, or seborrheic dermatitis requiring topical treatment to the scalp, significant trauma to the scalp, or untreated actinic keratosis on the scalp at Screening and/or Baseline.

5. Known history of moderate to severe androgenic alopecia or pattern hair loss prior to alopecia areata.
6. Unwilling to maintain a consistent hair style, including shampoo and hair products (including hair dye, process, and timing to visits), and to refrain from weaves or extensions throughout the course of the study, or shaving of scalp hair for at least 2 weeks prior to a SALT assessment.
7. Use of adhesive wigs, other than banded perimeter wigs, during the study.
8. History of a lymphoproliferative disease or malignancy with recurrence within the 5 years prior to the first study drug administration, other than non-melanoma skin cancer or cervical carcinoma. Patients with 3 or more basal or squamous cell carcinomas diagnosed in the past 2 years are excluded.
9. Atypical nevi or cutaneous lesions that are undiagnosed but suspicious for malignancy.
10. History of solid organ or hematological transplantation.
11. Systemic or invasive infection, as evidenced by fever, inflammation, or systemic signs of illness (e.g., malaise, myalgia, specific symptoms like pain, shortness of breath) within 2 weeks prior to first dose of study drug.
12. Abnormal levels of thyroid stimulating hormone at Screening, defined as $<0.9 \times$ the lower limit of normal (LLN) and $>1.2 \times$ the upper limit of normal (ULN).
13. Screening labs outside the normal range for parameters associated with potential risk for treatment under investigation. This will include but is not limited to:
 - a. Platelets $\leq 120 \times 10^9/L$ or $\geq 600 \times 10^9/L$
 - b. Absolute neutrophil count $\leq 1.5 \times 10^9/L$
 - c. Hemoglobin levels $\leq 11 \text{ g/dL}$ for females, or hemoglobin levels $\leq 12.5 \text{ g/dL}$ for males
14. Screening blood glucose levels of hemoglobin A1c $\geq 6.5\%$ (48 mmol/mol).
15. Abnormal liver function at Screening, defined as $\geq 2 \times$ ULN of any 3 or more of the following: serum alanine transaminase, serum aspartate transaminase, serum alkaline phosphatase, total bilirubin.
16. Abnormal renal function (estimated glomerular filtration rate $<60 \text{ mL/min}/1.73 \text{ m}^2$ using the MDRD equation).
17. At screening, any active or previous Hepatitis B or C infection, or known human immunodeficiency virus infection.
18. Vaccination with herpes zoster vaccine or any live virus vaccine within 6 weeks prior to Screening or during the study.
19. Positive TB test, or history of incompletely treated or untreated tuberculosis.

NOTE: In cases where performance of a QuantiFERON-TB Gold test is not possible, testing with a Tuberculin Skin Test (TST) may be an option after consultation with the Medical Monitor. If the TST is negative, patients can be randomized into the study, assuming they meet all other inclusion and none of the exclusion criteria. If results are

equivocal, or there is reason to believe the result is a false positive, a QuantiFERON-TB Gold must be performed before a subject is eligible for randomization.

20. Prolonged QT or heart-rate corrected QT (QTc) interval with Fridericia's correction (QTcF) > 450 msec for males or QTcF > 470 msec for females.
21. History of alcohol, medication, or illicit drug abuse within 1 year before the first dose of study drug.
22. Females who are nursing, pregnant, or planning to become pregnant while in the study, and for 30 days after last dose of study medication.
23. Participation in another investigational study within the greater of 4 weeks or 5 half-lives of an investigational medication prior to screening or during the study.
24. Use of strong CYP3A4 inhibitors (such as, but not limited to clarithromycin, conivaptan, grapefruit juice, indinavir, itraconazole, ketoconazole, lopinavir/ritonavir, mibefradil, nefazodone, nelfinavir, posaconazole, saquinavir, telaprevir, telithromycin, voriconazole, or fluconazole).
25. Use of strong CYP3A4 inducers (such as, but not limited to barbiturates, carbamazepine, efavirenz, glucocorticoids, modafinil, nevirapine, oxcarbazepine, phenobarbital, phenytoin, pioglitazone, rifabutin, rifampin, St. John's Wort, or troglitazone).
26. Donation of blood within a month of first dose of study drug or at any point throughout the study and for 30 days after last dose of study medication.
27. Clinically significant medical condition, psychiatric disease, or social conditions that, as determined by the Investigator, may unfavorably alter the risk-benefit of study participation, adversely affect study compliance, or confound interpretation of study results.

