Concomitant medications ¹³	X	X	X	X	X	X	X	X

HBV= hepatitis B virus; HCV = hepatitis C virus

¹ Randomization/Day 1 may occur any time after Screening laboratory results are available and reviewed by the Investigator.

² All subsequent visits and week increments should be based on the date of Visit 2. All visit windows are ± 3 days.

³ Also serves as the Early Termination Visit for patient withdrawal in this period.

⁴ The Safety Follow-Up Visit is intended for those patients who do not roll over into an open-label extension and for patients who have been discontinued from the study and completed the Early Termination Visit (Week 24).

⁵ Serum pregnancy test for females of childbearing potential only.

⁶ Urine pregnancy test should be performed at the randomization visit.

⁷ Includes hematology and serum chemistry.

⁸ Collected pre-dose, except on Visit 11.

⁹ Will include thyroid stimulating hormone and hemoglobin A1c at Screening only.

¹⁰Includes total cholesterol, low-density lipoprotein, high-density lipoprotein, and triglycerides.

¹¹ Should be performed by the same rater for the patient for the duration of the study.

¹²Sites will take photographs of patient's scalps and eyebrow/eyelashes, if involved, to provide visual support of baseline SALT as well as potential SALT changes throughout the study.

¹³Collection is ongoing.

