Patient safety will be monitored throughout the trial. The patient will be tested to ensure they do not have the Hepatitis B or C virus, thyroid function abnormalities or latent or active Tuberculosis, during the screening period. During the first 8 weeks of the Treatment Period, hematology and serum chemistry will be conducted every 2 weeks, followed by an assessment every 4 weeks thereafter through completion of the study at 24 weeks. Lipid levels will be assessed every 12 weeks throughout the Treatment Period. Significant cytopenias or other hematologic abnormalities will be managed by severity through dose interruption, or discontinuation, and signs and symptoms of infection will be closely monitored and treated promptly. Patients who experience intolerable symptoms during treatment may discontinue the study at the discretion of the Investigator. Patients may withdraw consent at any time. The Treatment Period will last 24 weeks to assess BID and QD doses, in parallel. Assessment of treatment response with SALT for efficacy will occur at 4, 8, 12, 16, 20 and 24 weeks. Upon completion of the 24-week Treatment Period patients will be eligible to either complete

treatment and exit the study following the safety follow-up visit, or roll-over into a long-term open-label extension study.

Approximately 60 patients are planned to be enrolled in the study; approximately 30 patients per dosing regimen.

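### Exclusion 12 joins its low and high TSH limits with *and*, so read literally no value can meet it, contrary to the stated purpose of the thyroid screen

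*Protocol*

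**What the plan says.** Exclusion 12 in Protocol Section 7.2 begins "Abnormal levels of thyroid stimulating hormone at Screening, defined as $<0.9 \times$ the lower limit of normal (LLN") and joins the upper limit to it as follows: "the lower limit of normal (LLN) and $>1.2 \times$ the upper limit of normal (ULN"). The synopsis prints exclusion 12 in the same words.

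Section 7 sets how the list operates: patients "must meet all of the following inclusion criteria and none of the exclusion criteria". A patient is therefore kept out by an exclusion criterion only if its terms are met.

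The purpose is stated twice. Protocol 6.3 lists, among the conditions to be ruled out by testing, "thyroid function abnormalities or latent or active Tuberculosis, during the screening period". SAP 2.2 repeats this: "The patient will be tested to ensure they do not have the Hepatitis B or C virus, thyroid function abnormalities". SAP 2.3 gives no TSH rule of its own and sends the reader to Protocol 7.1 and 7.2 for the full criteria.

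The footnote on clinical laboratory testing in the Protocol's Schedule of Events (Table 1) gives the timing: "Will include thyroid stimulating hormone and hemoglobin A1c at Screening only".

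The next criterion in the same list also has a low and a high limit, and joins them differently: "Platelets $\leq 120 \times 10^9/L$ or $\geq 600 \times 10^9/L".

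**The concern.** Exclusion 12 is the only criterion that names a thyroid test, and it is meant to be an objective threshold. If its two limits must hold together, nothing meets it and it does no work.

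Two things are at stake. The first is consistency of enrolment: about 10 sites apply the list, and a rule that has to be corrected in the reading may be corrected at one site and not at another. The second is the handling of deviations. SAP 5.2 has the sponsor classify protocol deviations as minor or major before database lock. If a patient with a clearly out-of-range TSH was randomised, whether that is a deviation from exclusion 12 depends on which reading is taken, and the text as printed supports the answer that it is not.

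**Working it through.** The plan gives no figure to reproduce here. The check is one of logic.

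**Inputs.** Low limit: TSH < 0.9 × LLN. High limit: TSH > 1.2 × ULN. Connector: *and* (Protocol 7.2 and synopsis, exclusion 12). Rule of operation: excluded only if a criterion is met (Protocol Section 7). The documents give no TSH reference range.

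**Step 1: the literal reading.** Let x be the screening TSH. Both conditions together require

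1.2 × ULN < x < 0.9 × LLN.

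Such an x exists only if 1.2 × ULN < 0.9 × LLN, that is, ULN / LLN < 0.9 / 1.2 = 0.75. In any reference range ULN > LLN > 0, so the ratio exceeds 1. The set is empty whatever range the laboratory uses.

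**Step 2: numerical confirmation.** A grid of 1,000,001 values from 0 to 100 was tested against five assumed reference ranges, two of them deliberately narrow. The counts under *either limit* depend on the width of the grid. They show only that the set is not empty.

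| Assumed LLN to ULN | Values meeting both limits | Values meeting either limit |
|---|---|---|
| 0.1 to 0.2 | 0 | 998,501 |
| 0.3 to 4.0 | 0 | 954,700 |
| 0.4 to 4.5 | 0 | 949,601 |
| 0.5 to 5.0 | 0 | 944,500 |
| 1 to 1.0001 | 0 | 996,999 |

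**Step 3: what happens to a clearly abnormal value.** A TSH of 3 × ULN meets the high limit (3 > 1.2) but not the low one. A TSH of 0.1 × LLN meets the low limit (0.1 < 0.9) but not the high one. Each meets one limb of the criterion. It is the conjunction that fails, so neither patient is excluded by no. 12 as printed.

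**Step 4: comparison within the list.** Criterion 13a would be just as empty if its platelet limits, at or below 120 and at or above 600, were joined by *and*. It joins them with *or*, so either limit alone excludes.

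**Step 5: comparison with the purpose.** Protocol 6.3 and SAP 2.2 say the test is there to make sure patients have no thyroid abnormality. A criterion that no value can meet cannot serve that purpose. The synopsis and Section 7.2 agree word for word on this item, so there is no second version in the documents to fall back on.

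**The case against.** The strongest reply is that no sensible site would read the criterion literally. It speaks of abnormal levels in the plural and then names a low range and a high range, which is a familiar loose way of listing two abnormal ranges. The conjunction is impossible, so a site has good reason to reject it, and Protocol 6.3 tells the site what the test is for. This largely stands as a forecast of practice: many sites would probably apply it as either/or. It does not make the text right, and eligibility should not rest on each site making the same silent correction.

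The second reply is that other routes remain. Exclusion 13 opens broadly, with "Screening labs outside the normal range for parameters associated with potential risk for treatment under investigation", and its list is expressly not exhaustive. Exclusion 27 lets the investigator exclude for a clinically significant condition. Protocol 9.9 requires the investigator to assess the screening laboratory results for eligibility, and Section 6.4 has eligibility reviewed again on Day 1. This also stands in part. A reader might infer that patients with abnormal TSH would pass unchecked into the trial, and the documents do not support that. But these routes turn on judgement and none of them names TSH, so they do not replace a stated threshold.

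Three further inferences are tempting and should not be drawn.

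- Measuring TSH only at Screening is not itself a fault. That is ordinary for an eligibility test.
- The passage in Protocol 9.1 on other causes of hair loss does not mention thyroid disease, so it cannot be used to argue that an abnormal TSH would confound the SALT score.
- Eligibility is settled before 1:1 randomisation, so nothing here steers such patients to one arm, and no bias in the comparison of regimens is shown.

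**Conclusion.** The wording is wrong as it stands. Taken exactly as printed, exclusion 12 excludes no possible TSH value, and this conflicts with the purpose stated in Protocol 6.3 and SAP 2.2. The conclusion rests only on the printed connector, on the rule in Section 7 that a criterion must be met to exclude, and on ULN being greater than LLN. It does not depend on any assumed reference range.

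The practical size is modest and cannot be quantified. A reader might want to turn it into a count of affected patients, but the documents give neither the frequency of abnormal TSH among those screened nor the number to be screened. The planned 60 is the number enrolled, which is not the right base. Any count would also have to assume that every site reads the criterion literally and that no investigator uses the discretionary routes. No endpoint, confidence interval or sample-size statement depends on TSH.

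What remains is an operative eligibility rule that fails if followed to the letter, with room for uneven application across sites and for dispute when deviations are classified.

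**What to change.** Reconcile the connector in exclusion 12 with the purpose stated in Protocol 6.3 and SAP 2.2 and with the form already used in 13a, where reaching either limit is enough. Make the same change in Section 7.2, in the synopsis and in any eligibility checklist drawn from them. Leave the multipliers 0.9 and 1.2 as they are; nothing here questions them. If patients have already been randomised, record in the pre-lock deviation review which reading was applied, so that classification under SAP 5.2 is consistent.

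The cost is one word in two places, carried in the next amendment, plus the checklist. The only foreseeable downside is a few more screen failures at any site that had been applying the literal reading.
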